5.5 Informed consent

Due to the fact, that the patients are regularly expected to be unconscious at the time of evaluation for va-ECMO and thus for inclusion in our study and any delay e.g. for consultation of a legal representative is not feasible in an emergency context, the primary inclusion into the study goes in accordance with the clinical criteria stated above. A retrospective informed consent has to be sought at the earliest possible moment from a legal representative or the patient itself, should the latter regain sufficient consciousness. In case of secondary disapproval and thus, drop-out from the study, samples and data gathered up to that time are handled in accordance with state and federal German law. This procedure has specifically been evaluated and approved by the responsible ethics committee.

5.6 Randomization

Randomization is performed at the time of establishment of va-ECMO. Drawing without returning of prepared sealed envelopes will ensure an identical size of 20 participants each for control and intervention groups .

5.7 Clinical anaethesiologic and intensive Care of the Participants

The general anaethesiologic and intensive care is not affected by inclusion into this study. All procedures are conducted in accordance with therapeutic standards of our hospital, referencing best medical practice and applicable guidelines.

The sample size to analyze the cytokine levels is estimated to amount to 5ml per time point.

5.7. Statistical analysis

Statistical analysis is conducted using the software package SPSS. To characterize the patients, we are going to conduct descriptive analytics in dependence on the statistical distribution of variables.

Continuous variables like hemodynamic and laboratory parameters are analyzed using a multifactorial ANOVA or a mixed lineary model.

Nominal or categorized variables are going to be analyzed in four-to-multi-square-tables with chi-square-tests or Fisher's exact test.

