In this study, we aim to show that hemoadsorption (Cytosorb®) is a viable option to reduce serum levels of proinflammatory cytokines in patients under va-ECMO after CPR. Specifically, our hypothesis constitutes significantly lower levels of IL-6 and TNF- α in patients undergoing hemoadsorption for 48 hours compared to a control group receiving standard medical care at va-ECMO during a 72 hours-timeframe.

Primary outcome parameters

Laboratory parameters expressing an inflammatory response constitute the primary outcome of our study. Thus,

IL-6, TNF-a, S1P, PCT, CRP, leucozytes

are to be measured at time points 0,6,12,24,48 and 72 hours after administration to va-ECMO.

Secondary outcome parameters

Those are supposed to reflect secondary and tertiary effects of the hemoadsorption on organ function and overall survival of the patients:

- 1. Laboratory and clinical parameters of inflammation and organ damage/dysfunction (cardiovasculary, pulmonary, hepatic, renal, neuronal):
 - NSE, (free) hemoglobine, haptoglobine, BNP, Troponine, Creatinekinase, Myoglobin, GOT, GPT, Creatinine
 - cardiovasculary: (MAP, CVP, HR,. echocardiographic parameters)
 - pulmonary: oxygenation/decarboxylation, acid-base-balance by blood gas analysis

- 2. Parameters of treatment:
 - Cardiovasculary: Dependence on inotropics, and vasopressors, volume substitution or elimination,
 - pulmonary: relevant parameters of ventilation
 - additional organ replacement therapy (dialysis, hepatic replacement)
- 3. Parameters of terminal outcome
 - mortality within the first 30 days after inclusion into the study
 - length of stay in intensive care/in hospital

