5.3 Sample size

We expect a difference of 20-30% in serum concentration of IL-6 at 24 hours after inclusion (about 60µg/L difference at total levels of 200-300µg/L, standard deviation 90µg/L). With 18 patients per group, the study could determine a significant difference between the groups with a power of 90% and an error propability of 5% by ANOVA. To attribute for post-hoc exclusion or drop-out of participants with an estimated rate of 10%, we suggest a sample size of 20 patients per group, adding to a total of 40 participants in the study

This calculation is based on the publication of Adrie C. Et al. (1) and on a previous study performed in our department (publication pending).

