5.8. Time points and parameters

Time points:

- 1) on administration to va-ECMO
- 2) 6 hours post administration to va-ECMO
- 3) 12 hours post administration to va-ECMO
- 4) 24 hours post administration to va-ECMO
- 5) 48 hours post administration to va-ECMO
- 6) 72 hours post administration to va-ECMO

Parameters

- 1. inflammatory:
 - IL-6
 - TNFα
 - S1P
 - PCT
 - CRP
 - leukozytes
- 2. cardiocirculatory
 - MAP, CVP, HR
 - Dependence on external inotropes or vasopressors
 - BNP, Troponine, Creatinekinase, Myoglobine, Haptoglobine
 - echocardiographic parameters
- 3. gas exchange in arterial blood gas analysis
 - partial pressures of Oxygen and Carbon dioxide
 - pH and lactate
 - Base excess
- 4. hepatic
 - GOT, GPT
- 5. renal
 - diuresis
 - fluid balance
 - serum creatinine
 - glomerularic filtration rate estimated by CKD-EPI-formula

Additionally, we are going to evaluate demographic data (functional status in accordance with ASA-classification, age, sex, size, total body weight) and periprocedural parameters with specific focus on CPR (duration/time prior to va-ECMO, cause of arrest).

Overview of the study

Principal investigator	[name]. [name]
Title	HaemoAdsorption Nach Reanimation An ECMO (HANRAE)
Hypothesis	Additional hemoadsorption (Cytosorb®) in the extracorporal
	circulation established by va-ECMO in patients after cardiac arrest
	and CPR reduces the levels of IL-6 and TNF α in the serum.
Target population	Patients under va-ECMO subsequent to cardiac arrest and CPR
Primary endpoints	Levels of IL-6 und TNF α in the patients' serum in an interval of 72
	hours post resuscitation
Secondary endpoints	• Laboratory and clinical parameters of inflammation and
	organ damage/dystunction (cardiovascular, pulmonary,
	 Parameters of intensive care treatment (e.g. ventilation)
	additional organ replacement therapy)
	 Parameters of terminal outcome (mortality)
study design	single-centerd prospective controlled randomized
inclusion criteria	 Age ≥ 18 years
	cardiac arrest with CPR
	application of va-ECMO for insufficient spontaneous
	circulation
exclusion criteria	contraindication for va-ECMO in accordance with the
exclusion cinteria	standard operating procedures of the University Cardiac
	Arrest Center Hamburg ECMO bei Reanimation – see 5.4
	for details
sample size	We expect a difference of 20-30% in serum concentration of IL-6
	at 24 hours after inclusion (about 60µg/L difference at total levels

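### The 0 h sample is listed among the primary-outcome times although it coincides with randomisation; using it as a baseline covariate would gain precision at almost no cost

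*Protocol*

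**What the plan says.** Protocol section 5.1 states: "Laboratory parameters expressing an inflammatory response constitute the primary outcome of our study". It names IL-6, TNF-alpha and four further markers, which "are to be measured at time points 0,6,12,24,48 and 72 hours after administration to va-ECMO". The 0 h time has the same standing there as the five later ones.

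Section 5.6 says: "Randomization is performed at the time of establishment of va-ECMO". Section 5.8 defines the first time point as "on administration to va-ECMO". The two therefore nominally coincide.

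The adsorber is described in section 3 as a module added to the va-ECMO system. The hypothesis in the overview table places it in the extracorporeal "circulation established by va-ECMO in patients after cardiac arrest". Adsorption cannot start before va-ECMO does. The protocol does not say whether the 0 h blood is drawn before the adsorber is started.

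On analysis, section 5.7 says: "Continuous variables like hemodynamic and laboratory parameters are analyzed using a multifactorial ANOVA or a mixed lineary model". It names no baseline term. Section 5.3 sizes the trial on the IL-6 difference at 24 h and claims that "the study could determine a significant difference between the groups with a power of 90% and an error propability of 5% by ANOVA". The overview table defines the primary endpoint as levels of IL-6 and TNF-alpha "in the patients' serum in an interval of 72" hours.

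**The concern.** A sample taken at randomisation, before adsorption can have acted, is not expected to carry a treatment effect. Listing it as a primary-outcome time has two possible consequences.

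- **The baseline is unused in the quantified comparison.** The 24 h ANOVA in section 5.3 takes no account of the patient's own starting value, although that sample is scheduled for everyone. In a trial of 40 patients, any variance it explains is worth having.
- **The baseline may be used badly.** If 0 h enters the model as one more outcome time, an overall group effect is diluted by a time at which no difference is expected. If instead the change from 0 h to 24 h is compared between groups, the noise of the 0 h value is added. With equal SDs, that is worse than ignoring 0 h whenever the correlation is below 0.5.

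Section 5.7 is open enough to permit the good use and both poor ones.

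**Working it through.** **Inputs.** From section 5.3: difference δ = 60 µg/L, SD σ = 90 µg/L, n = 18 evaluable per arm (20 randomised). Assumed: a two-sided 5% test, because sidedness is not stated, and a 0 h–24 h correlation r, which the protocol does not give and which is therefore varied.

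**1. The plan's own comparison.** A two-group ANOVA is a t-test. The standard error is 90 × √(2/18) = 30, so the noncentrality is 60/30 = 2.0 on 34 df. Power is **49.3%**, not the stated 90%. That discrepancy is a separate matter; 49.3% is the reference value here. With 20 per arm (38 df), power is 53.8%.

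**2. Adjusting for 0 h.** With the slope estimated, the variance of the adjusted difference is σ²(1 − r²)(2/n)(1 + T²/(2n − 2)). T is the t statistic for the chance imbalance in the 0 h value and follows a t distribution on 2n − 2 df. Power is the noncentral t probability on 2n − 3 df, averaged over T. For the expected 95% CI half-width, the true SD is used.

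| r | Power, 18 per arm | Power, 20 per arm | CI half-width, 18 per arm (µg/L) | Relative to unadjusted |
|---|---|---|---|---|
| unadjusted | 49.3% | 53.8% | 61.0 | 1.00 |
| 0 | 48.2% | 52.7% | 62.0 | 1.016 |
| 0.1 | 48.5% | 53.1% | 61.7 | 1.011 |
| 0.3 | 51.8% | 56.5% | 59.1 | 0.970 |
| 0.5 | 59.8% | 64.8% | 53.7 | 0.880 |
| 0.7 | 76.4% | 81.0% | 44.3 | 0.726 |

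Adjustment breaks even at r = 0.175 with 18 per arm and at r = 0.165 with 20. In terms of patients, 18 per arm with adjustment are worth 19.1, 23.0 and 33.2 per arm without it at r = 0.3, 0.5 and 0.7.

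The result does not depend on the SD at 0 h. Simulation with 40,000 trials per cell, and a 0 h SD equal to, half or twice the 24 h SD, gave 52%, 59–60% and 76–77%.

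**3. Change from 0 h instead.** With equal SDs the variance per patient is 2σ²(1 − r). Power at 18 per arm is 37.6, 49.3 and 70.8% at r = 0.3, 0.5 and 0.7. If the 0 h SD is half the 24 h SD, the figures are 51.4, 61.2 and 74.5%. The change score therefore depends on the SD ratio as well as on r.

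**4. 0 h kept as an outcome time in an overall group effect (illustration).** Assume an effect of 60 at each of the five later times, none at 0 h, and the same correlation r between all times.

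- Including 0 h, the mean effect is 60 × 5/6 = 50 and the SD of a patient's mean is 90√((1 + 5r)/6).
- Leaving 0 h out, the effect is 60 and the SD is 90√((1 + 4r)/5).
- With 0 h as covariate, the effect is 60 and the SD is 90√((1 + 4r)/5 − r²), with the slope estimated as in step 2.

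| r | 0 h as outcome | 0 h omitted | 0 h as covariate |
|---|---|---|---|
| 0.3 | 71% | 83% | 90% |
| 0.5 | 56% | 71% | 90% |
| 0.7 | 46% | 61% | 96% |

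**5. TNF-alpha.** The protocol gives no SD or difference, so power cannot be computed. The relative CI widths in step 2 hold for any marker: 3, 12 and 27% narrower at r = 0.3, 0.5 and 0.7, and 1–2% wider at r = 0 to 0.1.

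**The case against.** The strongest reply is that model terms belong in the statistical analysis plan, which is not at hand. Section 5.7 does not exclude a baseline term, and either model it names can carry one. Section 5.1 can be read as a sampling schedule, since section 5.8 repeats the same six times for all parameters. Sizing a trial on an unadjusted comparison is ordinary practice when no correlation is known and does not commit the analysis to be unadjusted. No passage proposes a change score.

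Much of this stands. The protocol does not forbid the better analysis, and steps 3 and 4 describe readings it leaves open, not analyses it prescribes. What remains is that the protocol itself fixes the list of primary-outcome times and puts a randomisation-time sample on it without distinction. Whether the 0 h draw precedes the adsorber is also a sampling matter that no later analysis can repair.

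A second reply is that the benefit rests on an unknown correlation. Section 3 attributes the inflammatory reaction to ischaemia and reperfusion, so a value taken at va-ECMO start may precede much of the response seen at 24 h. The correlation could then be low, and between 0.1 and 0.3 the change in power is only −0.8 to +2.5 points. This is a fair caution and stands. It limits the expected gain but does not reverse the advice, because the worst loss is about one point.

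Finally, requiring the draw before adsorber start is a small procedural condition in an emergency setting, and some 0 h samples may be missed. That is also fair, and the fix allows for missing values.

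**Conclusion.** The concern holds as an improvement the sponsor should make; it is not a validity error. Section 5.1 lists 0 h as a primary-outcome time, sections 5.6 and 5.8 put it at randomisation, and section 5.7 assigns it no baseline role.

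For IL-6 at 24 h with 18 per arm, adjustment moves power by between −1.2 points (r = 0) and +27 points (r = 0.7). This rests on the protocol's SD and difference, a two-sided 5% test and an assumed correlation. Confidence in the size is moderate because nothing in the protocol indicates where in that range the correlation lies. The gain is in precision only: randomisation already protects the comparison from bias, and the shortfall from the stated 90% power needs its own correction.

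**What to change.** In sections 5.1 and 5.8, label 0 h as the baseline, drawn before the adsorber is started, and list 6, 12, 24, 48 and 72 h as the outcome times.

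In section 5.7, replace the open choice for the laboratory markers with wording such as: *IL-6, TNF-alpha and the other laboratory markers are analysed by a linear mixed model on the 6–72 h samples with group, time, group × time, the patient's 0 h value of that marker, and 0 h value × time; if 0 h values are missing, an equivalent constrained-baseline model is used.* The 24 h IL-6 difference on which section 5.3 is sized is then baseline-adjusted, and the 0 h value × time term lets the baseline slope weaken at later times if the correlation decays.

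The cost is wording in three sections and attention to the order of the 0 h draw and adsorber start. No patients or samples are added. The statistical price is one slope per outcome time, at most 1.2 points of power at 24 h (49.3% to 48.2%) if the correlation is zero.

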5.8. Time points and parameters

Time points:

- 1) on administration to va-ECMO
- 2) 6 hours post administration to va-ECMO
- 3) 12 hours post administration to va-ECMO
- 4) 24 hours post administration to va-ECMO
- 5) 48 hours post administration to va-ECMO
- 6) 72 hours post administration to va-ECMO

Parameters

- 1. inflammatory:
 - IL-6
 - TNFα
 - S1P
 - PCT
 - CRP
 - leukozytes
- 2. cardiocirculatory
 - MAP, CVP, HR
 - Dependence on external inotropes or vasopressors
 - BNP, Troponine, Creatinekinase, Myoglobine, Haptoglobine
 - echocardiographic parameters
- 3. gas exchange in arterial blood gas analysis
 - partial pressures of Oxygen and Carbon dioxide
 - pH and lactate
 - Base excess
- 4. hepatic
 - GOT, GPT
- 5. renal
 - diuresis
 - fluid balance
 - serum creatinine
 - glomerularic filtration rate estimated by CKD-EPI-formula

Additionally, we are going to evaluate demographic data (functional status in accordance with ASA-classification, age, sex, size, total body weight) and periprocedural parameters with specific focus on CPR (duration/time prior to va-ECMO, cause of arrest).

Overview of the study

Principal investigator	[name]. [name]
Title	HaemoAdsorption Nach Reanimation An ECMO (HANRAE)
Hypothesis	Additional hemoadsorption (Cytosorb®) in the extracorporal
	circulation established by va-ECMO in patients after cardiac arrest
	and CPR reduces the levels of IL-6 and TNF α in the serum.
Target population	Patients under va-ECMO subsequent to cardiac arrest and CPR
Primary endpoints	Levels of IL-6 und TNF α in the patients' serum in an interval of 72
	hours post resuscitation
Secondary endpoints	• Laboratory and clinical parameters of inflammation and
	organ damage/dystunction (cardiovascular, pulmonary,
	 Parameters of intensive care treatment (e.g. ventilation)
	additional organ replacement therapy)
	 Parameters of terminal outcome (mortality)
study design	single-centerd prospective controlled randomized
inclusion criteria	 Age ≥ 18 years
	cardiac arrest with CPR
	application of va-ECMO for insufficient spontaneous
	circulation
exclusion criteria	contraindication for va-ECMO in accordance with the
exclusion cinteria	standard operating procedures of the University Cardiac
	Arrest Center Hamburg ECMO bei Reanimation – see 5.4
	for details
sample size	We expect a difference of 20-30% in serum concentration of IL-6
	at 24 hours after inclusion (about 60µg/L difference at total levels
	of 200-300µg/L, standard deviation 90µg/L). With 18 patients per
	group, the study could determine a significant difference between
	the groups with a power of 90% and an error of propability of 5%
	by ANOVA.
	To attribute for post-hoc exclusion or drop-out of participants, we
	suggest a sample size of 20 patients per group, adding to a total of
	40 participants in the study.
randomization	Randomization is performed as drawing without returning to
	ensure an identical size for control and intervention groups

Hamburg, 29.12.2017

6. Literature

6. Bernardi MH, Rinoesl H, Dragosits K, Ristl R, Hoffelner F, Opfermann P, et al. Effect of hemoadsorption during cardiopulmonary bypass surgery - a blinded, randomized, controlled pilot study using a novel adsorbent. Critical care. S016;20:96.
